## Secondary Outcome Measures\*\*

- 1) ECG and skin temperature confirmation
  - Confirm that ECG characteristics align with those from bench results using a simulator
  - Confirm that skin temperature readings align with those from bench results

\* Note that in the pathologic cohort of subjects, RR and rTV are NOT designed to be a primary method of validating the CPM System but are included in the data collection and analysis protocols.

\*\* Note that the secondary objectives and outcome measures only apply to the pathologic cohort of subjects and are NOT designed to be a primary method of validating the CPM System. These objectives and outcome measures are meant to gather more data in a controlled setting since the devices used to measure these specific parameters will already be used in the study.

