## Secondary Objectives\*\*

1) Confirm the accuracy of the skin temperature and ECG capabilities of the CPM System

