## **CPM System Raw and Derived Measurements:**

The CPM Analytics Engine derives measurements such as heart rate, respiration rate, relative tidal volume, thoracic impedance, body posture, diastolic heart sounds, QT and QRS widths, and cardiac abnormalities from raw measurement data acquired from the CPM device's sensors and electrodes. The raw measurements taken by the device and their derived parameters are illustrated in the graphic below. For this study, the focus will be on the raw impedance spectroscopy and streaming impedance measurements and the respective derived parameter measurements from each of these raw parameters. Raw and derived ECG and temperature parameters will also be confirmed.

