## **Reference Devices:**

The MGC Diagnostics Ultima CPX metabolic cart will be used as a reference device to measure reference tidal volume and respiration rate (as well as ECG in the pathologic cohort). This device includes capnography and spirometry in addition to a pneumotachograph function.

The UFI Model 2994D THRIM (Tetra-Polar High-Resolution Impedance Meter) will be used as a reference device to validate the Thoracic Impedance measurement.

A clinical grade non-contact IR temperature sensor will be used to gather skin temperature data.

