The exercises below will then be followed, with the time of the start of each exercise recorded in the CRF. Each exercise will last approximately 2 minutes, or the time that it takes to complete one full measurement with the CPM device in measurement mode (initiated by the CPM mobile app). Reference bioimpedance will be denoted at the beginning of each measurement in both a sitting and laying down position, following the CPM Device measurement flow. All CPM Device measurements include both a Fowler and a Supine portion.

Participants will be asked to breathe normally throughout the course of all measurements, including during the final three measurements which include the use of a device that tracks respiration rate and tidal volume. Reference devices to measure skin temperature and ECG will also be used during clinic visit two, before and after the CPM Device usage.

Subjects are to be instrumented with both the ADI device and reference impedance, mouthpiece, pneumotach, sampling line for O2 and CO2, ECG, and skin temperature.

Item	Description	Device/Mode	Duration	
1	Baseline reference TI measurement*	Bioimpedance reference	1 min	
2	Baseline measurement	CPM/Baseline Setup, App	3 min	
3	Reference TI measurement	Bioimpedance reference	1 min	
4	Application 1/Measurement 1**	CPM/Patient, App	2 min	
5	Application 1/Measurement 2	CPM/Patient, App	2 min	
6	Application 1/Measurement 3	CPM/Patient, App	2 min	
7	Reference TI measurement	Bioimpedance reference	1 min	
8	Application 2/Measurement 1	CPM/Patient, App	2 min	
9	Application 2/Measurement 2	CPM/Patient, App	2 min	
10	Application 2/Measurement 3	CPM/Patient, App	2 min	
t = 1 hour				
11	Reference skin temperature, ECG data	Reference temperature, ECG devices	1 min	

12	Reference TI measurement	Bioimpedance Reference	1 min
13	Application 3/Measurement 1; RR/TV	Reference spirometer, CPM/Patient,	2 min
	measurement	Арр	
14	Application 3/Measurement 2; RR/TV	Reference spirometer, CPM/Patient,	2 min
	measurement	Арр	
15	Application 3/Measurement 3; RR/TV	Reference spirometer, CPM/Patient,	2 min
	measurement	Арр	
16	Reference skin temperature, ECG data	Reference temperature, ECG devices	1 min

\* Measurements with the bioimpedance reference device refer to the length of time that it takes to get a stable thoracic impedance reading in both a sitting and lying down position.

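### The ECG and skin temperature outcome names only bench results as its comparator, and no planned analysis uses the patient reference readings collected for both measures

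*Combined protocol and SAP*

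**What the plan says.** The Secondary Objectives section gives one aim: "Confirm the accuracy of the skin temperature and ECG capabilities of the CPM System". Secondary Outcome Measures turns it into two checks. For ECG: "Confirm that ECG characteristics align with those from bench results using a simulator". For temperature: "Confirm that skin temperature readings align with those from bench results". A simulator is mentioned for ECG only.

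A footnote there limits both the objective and the outcomes to the pathologic cohort and says they are not designed as a primary way of validating the system. It adds: "These objectives and outcome measures are meant to gather more data in a controlled setting". The reason given is that the devices measuring these parameters are in the study anyway.

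Reference Devices lists a metabolic cart for respiration ("as well as ECG in the pathologic cohort") and, for temperature, states: "A clinical grade non-contact IR temperature sensor will be used to gather skin temperature data". The pathologic study procedures add: "Reference devices to measure skin temperature and ECG will also be used during clinic visit two, before and after the CPM Device usage". In the table these are items 11 and 16, one minute each, on either side of CPM measurements 13 to 15.

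The section on raw and derived CPM measurements says "Raw and derived ECG and temperature parameters will also be confirmed" and gives no comparator or metric. The pathologic Effectiveness and Endpoint Analyses section names thoracic impedance and an R² for tidal volume. The pathologic Endpoints list covers impedance, respiration rate and tidal volume.

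**The concern.** The objective concerns accuracy, which is a question about error: how far the CPM reading lies from the true value in the person wearing the device. The only comparator that the outcome names is a result obtained on a bench. A bench run has its own input, so a patient reading may differ from it and be correct, or match it and be wrong.

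The information that bears on accuracy in patients is collected at visit two but has no stated role in the analysis. The Study Design section describes the study as preparation for a 510(k) submission. As written, a report could state that ECG and temperature were confirmed without any comparison against a patient reference, or the comparison could be chosen after the data are seen.

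**Working it through.** The plan gives no sample size, standard deviation, margin or threshold for ECG or skin temperature, so there is no figure to reproduce. The pathologic cohort's only sample size calculation is for impedance: (1.96 + 1.65)² × (5.1/6)² = 13.03 × 0.7225 = 9.42, rounded up to the stated 10. It has no bearing on this point. The check is therefore a comparison of the sections.

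**Step 1: what each comparison can show.** Write a CPM reading in a patient as T + e, where T is that patient's true value and e is the device error. Write a bench reading as B + b, where B is the bench input and b is the bench error.

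- Patient minus bench: (T − B) + (e − b). The term T − B is the gap between a patient and a test input. It is not zero by design and is not an error of the device.
- CPM minus patient reference, with reference error r: e − r, plus any real change in T between the two readings. T cancels when the readings are concurrent.

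Only the second comparison isolates device error in the patient, and the outcome names only the first. This is general reasoning, since the documents do not describe the bench tests.

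**Step 2: whether the reference readings have an analysis role.**

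| Section | ECG and skin temperature |
|---|---|
| Secondary Objectives | Accuracy to be confirmed |
| Secondary Outcome Measures | Comparator is bench (simulator for ECG) |
| Reference Devices | Cart for ECG, IR sensor for temperature |
| Pathologic procedures, items 11 and 16 | Reference readings taken |
| Pathologic Effectiveness and Endpoint Analyses | Not named |
| Pathologic Endpoints | Not listed |

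The agreement statistics in the analysis section are for pairs collected continuously with the CPM and a reference device. Items 11 and 16 are separate readings outside the CPM measurements, so they do not plainly fall under that wording. No ECG characteristic, agreement statistic or acceptance limit is named anywhere for these two measures.

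**Step 3: how much data there is.** Two scheduled reference readings in each of 20 subjects give 2 × 20 = 40 readings per parameter. They are clustered in 20 subjects and are not 40 independent comparisons.

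**Step 4: how well the readings pair.**

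- Item 12, a one-minute reference impedance reading in two positions, lies between items 11 and 13. Item 16 follows item 15 directly.
- Each CPM measurement covers sitting and lying, but no posture is stated for items 11 and 16.
- The site of the IR reading relative to the CPM temperature sensor is not stated.
- The procedures say in one place that ECG is fitted for the indicated items, and the table names ECG only at items 11 and 16. Elsewhere they list ECG among the equipment worn together with the mouthpiece and the CPM device. Concurrent ECG during items 13 to 15 is therefore possible but not established.

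**The case against.** The strongest reply is that the protocol claims little here. The footnote says that these measures are supportive, and the Background names respiration rate, relative tidal volume and thoracic impedance as the parameters to be validated clinically. A field check of functions already tested on the bench is a coherent, modest aim. This stands, and it sets the weight of the point. It does not repair the comparator. The footnote's reason, that the measuring devices are in the study anyway, points towards using the reference readings.

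A second reply is that alignment with bench results may mean that error against the patient reference should resemble the error seen on the bench. The text does not exclude this, but no section says it. That reading also needs the CPM-minus-reference difference in patients, which the plan never defines.

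A third reply is that silence in the analysis section is weak evidence, since respiration rate is not named there either. That is fair for the section alone. However, respiration rate has a criterion in the Endpoints list, whereas ECG and temperature appear in neither place.

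A reader might also infer that the sponsor has chosen bench values in place of the patient references and means to leave those readings unused. The documents do not support that: they are silent on how the readings will be used, and silence does not show an intention to discard them.

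**Conclusion.** The point holds as a mismatch between a supportive objective and its stated comparator, together with reference data that have no assigned analysis. It is more than missing detail, because the comparator that is named cannot answer an accuracy question. It is minor: it touches two secondary measures in one cohort of 20 and no primary endpoint, sample size or listed endpoint criterion.

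Two stronger readings should be avoided. One is that a simulator is the comparator for temperature; the protocol mentions a simulator for ECG only. The other is that 40 clean pairs are waiting to be analysed; they are clustered in 20 subjects, are not concurrent as scheduled, and have no stated posture or IR site.

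The conclusion assumes that a bench input is not tied to any patient's own value, and that the reference ECG yields at least some of the measures that the CPM derives. The documents confirm neither directly.

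**What to change.** Restate the outcome in Secondary Outcome Measures as the within-patient CPM-minus-reference difference in skin temperature and in those CPM-derived ECG measures (heart rate, QRS width, QT width) that the reference ECG also provides. Then:

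1. State whether reference ECG is recorded during items 13 to 15. If it is, use those concurrent readings.
2. Otherwise pair item 11 with item 13 and item 16 with item 15, matching posture where it is recorded. Use the same pairing for temperature, and record posture and the IR site on the CRF.
3. Report the mean difference, its SD and limits of agreement that account for repeated readings within the 20 subjects.
4. Either prespecify an acceptance limit for each measure or word the objective as descriptive.
5. Keep the bench results as context, and add ECG and temperature to the pathologic analysis section.

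The cost is wording, two CRF fields and one descriptive table, with no new visits, devices or patients. The drawback is that readings taken apart in time, with possible differences in posture or site, will widen the limits of agreement. The documents give no basis for estimating by how much.

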## **Background** (*Include relevant experience, gaps in current knowledge, preliminary data, etc.*):

The Cardio-Pulmonary Management (CPM) System is intended for use in adults undergoing monitoring for cardiopulmonary conditions under the direction of a licensed medical professional to measure, record, and periodically transmit physiological data. One of the main challenges in managing these patients' care with the current standard of care lies in providing health care providers with insight on how patients are trending once diagnosed, and (post-discharge) identifying patients who are at high risk for an adverse event, so that these patients can be treated prior to being admitted or re-admitted to the hospital.

Studies such as MultiSENSE in 2017 have demonstrated, using a large cohort of patients implanted with a CRTD device, that it is possible to predict clinical decompensation (in this case, related to heart failure) using a combination of relevant parameters that include heart sounds, thoracic impedance, respiration, heart rate, and activity (Boehmer et al., 2017). Measurement and monitoring devices are important tools used to manage these at-risk populations; however, there are limited options that provide multi-parameter and noninvasive patient data collected and analyzed within one device.

[figure not shown]
The ADI At-Home CPM System acquires physiological data and derived measurements associated with the presence and progression of cardiopulmonary conditions, including S3 heart sound, respiratory rate and relative changes in tidal volume, changes in thoracic impedance, and electrocardiogram abnormalities. The end goal of the product is to collect, derive and transmit these measurements to the clinical care team daily and with high accuracy. These data enable the clinical care team to monitor their patients more closely, potentially resulting in more informed clinical management decisions and reducing the need for hospitalizations. This study aims to validate the accuracy of several of these parameters (respiration rate, relative tidal volume, and thoracic impedance) clinically, using both pathologic patients in the intended use population as well as healthy volunteers who will follow respiration patterns (changing rate and depth) mimicking those observed in patients with cardiopulmonary conditions.

## **Description of Investigational Device:**

The ADI At-Home CPM (Cardiopulmonary Management) System is a non-invasive device that measures and trends a variety of biological parameters. The device is battery-operated and biocompatible. The device is placed on the left chest area with one adhesive "island" on the sternum and the other island under the left arm (near the mid-axillary line). A round acoustic sensor falls near the apex of the heart, and for those with breast tissue, it is located similarly to the underwire of a bra. The device uses this sensor as well as five electrodes, an accelerometer, and a temperature sensor.

The device uses adhesive patches to adhere to the body. These use a gentle silicone adhesive with five hydrogel pads embedded (which align with the metal electrodes on the device). The device-side of the adhesives are composed of hook and loop material (like baby diapers) which allow the adhesives to be easily replaced when adhesion degrades.

During normal use, the device is only worn for about 5 minutes to acquire a single measurement. It is used with a Base Station that charges and stores the device and sends measurement data to the cloud. The CPM Device also has an alignment tool that is fitted to each patient and aids in proper repeatable placement of the device. In this clinical evaluation however, the study team will place the device on participants and will not use the base station hardware or alignment tool. Additionally, to ensure consistent placement position, the device will either be worn for the entire duration of the study to avoid changes in the device position throughout the visit (healthy cohort), or a skin marker will be used to locate the device for each placement (pathologic cohort).

#### **Intended Use:**

The ADI At-Home CPM (Cardiopulmonary Management) System is intended for adults undergoing monitoring for cardiopulmonary conditions under the direction of a licensed medical professional to measure, record, and periodically transmit physiological data.

The ADI At-Home CPM System is indicated for patients:

- Taking diuretic medication
- Living with heart failure
- Recovering from a coronary artery disease-related event
- Chronic Obstructive Pulmonary Disorder

[figure not shown]
The ADI At-Home CPM System is contraindicated for:

• Those patients requiring attended, in-hospital monitoring for life threatening arrhythmias

## **CPM System Raw and Derived Measurements:**

The CPM Analytics Engine derives measurements such as heart rate, respiration rate, relative tidal volume, thoracic impedance, body posture, diastolic heart sounds, QT and QRS widths, and cardiac abnormalities from raw measurement data acquired from the CPM device's sensors and electrodes. The raw measurements taken by the device and their derived parameters are illustrated in the graphic below. For this study, the focus will be on the raw impedance spectroscopy and streaming impedance measurements and the respective derived parameter measurements from each of these raw parameters. Raw and derived ECG and temperature parameters will also be confirmed.

## Respiration Rate and Tidal Volume Derivation:

Streaming of impedance is measured across the left side of the chest using 100kHz excitation frequency and streamed/sampled at a rate 50 samples per second.

An algorithm is used to process the stream of impedance data and extract changes in impedance caused by breathing (tidal impedance) that is used to track the relative changes in tidal volume of the subject. Similarly, the rate of these changes in thoracic impedance is used to calculate the respiration rate.

## *Thoracic Impedance and Delta Impedance Derivation:*

The CPM System collects impedance spectroscopy at a variety of frequencies in two positions (usually Supine and Fowler/sitting upright).

The magnitude of thoracic impedance, at 100kHz excitation frequency, is computed as the median of impedance in each body position. The impedance is derived from two different body positions and is displayed as Thoracic impedance (median of impedance in the position with lower tilt) and the change in thoracic impedance (the difference between those two positions, reported as " $\Delta Z$ ").

## **Reference Devices:**

The MGC Diagnostics Ultima CPX metabolic cart will be used as a reference device to measure reference tidal volume and respiration rate (as well as ECG in the pathologic cohort). This device includes capnography and spirometry in addition to a pneumotachograph function.

The UFI Model 2994D THRIM (Tetra-Polar High-Resolution Impedance Meter) will be used as a reference device to validate the Thoracic Impedance measurement.

A clinical grade non-contact IR temperature sensor will be used to gather skin temperature data.

## **Safety Equipment:**

[figure not shown]
A finger-worn SpO2 monitor will be used throughout the study exercises to ensure that subjects are receiving enough oxygen during the clinic visit.

#### **Study Design and Methods**

**Methods:** *Describe, in detail, the research activities that will be conducted under this protocol:* **Study Design:** 

[figure not shown]
This study is designed to be a clinical validation study to ready the CPM System for FDA 510(k) submission. This study will be conducted as a prospective non-randomized study with two study arms/cohorts – one of healthy adult patients, one of pathologic patients who fit into the intended use population of the CPM System. The study is non-significant risk, since the CPM Device is noninterventional and noninvasive. The study is designed to validate the accuracy of the respiration rate and relative tidal volume as well as the precision of the thoracic impedance measurement of the CPM system. All participants, regardless of the study arm they are a part of, will be fitted with both the CPM Device as well as reference devices.

## Healthy Cohort Study Activities

Page 6 of 24

# Pathologic Cohort Study Activities

# **Study Population and Sample Size:**

## Healthy Cohort

The target population for this cohort is healthy adult volunteers who do not have preexisting heart or lung conditions or illness. The goal is to recruit a participant population with a range of body types and BMIs and an approximately even split of genders.

## Pathologic Cohort

The target population for this cohort is adult patients who have been diagnosed with cardiopulmonary conditions. These can include chronic pulmonary conditions, chronic cardiac conditions, and those who are taking diuretic medications, living with heart failure, Chronic Obstructive Pulmonary Disorder (COPD), or recovering from coronary-artery disease related events. The goal is to recruit a participant population with a range of body types and BMIs and an approximately even split of genders as well as conditions outlined above (e.g. at least 5 each of COPD, HF, recovering from a coronary artery disease related event, and taking diuretic medication).

The minimum sample size for this study is 20 subjects per cohort (40 participants total), who will all complete the entirety of exercises included in the respective cohort's study protocol.

## **Study Duration:** *Healthy Cohort*

The duration per participant will be one supervised session of approximately two hours. At least one safety follow-up call will occur within one week of the in-clinic session.

## Pathologic Cohort

The duration per participant will be two supervised sessions of approximately one hour each. These two study sessions will take place within one day and will be separated by at least one hour. At least one safety follow-up call will occur within one week of the in-clinic session.

It is expected that the entire study duration, from the enrollment of the first participant to the completion of the final participant's site visit, will be approximately 12 weeks total, with 6 weeks allotted per cohort.

